APPENDIX E. ADMINISTRATION SITE REACTION GRADING AND MANAGEMENT

Grading:

- Grading should be done using two systems: Common Terminology Criteria for Adverse Event version 4.03 (which should be used for all dose delay/withdrawal decisions) and the system outlined below.
- Table: Administration Site Reaction Grading Scale (adapted from "FDA Guidance for Industry—Toxicity Grading Scale for Healthy Adult and Adolescent Volunteers Enrolled in Preventive Vaccine Clinical Trials")

Local Reaction to	Mild (Grade 1)	Moderate (Grade 2)	Severe (Grade 3)	Potentially Life
Injectable Product				Threatening
				(Grade 4)
Pain	Does not interfere	Repeated use of non-narcotic pain reliever > 24 hours	Any use of narcotic pain reliever or	Emergency room visit or
	with activity	or interferes with	prevents daily	hospitalization
		activity	activity	
Tenderness	Mild discomfort to touch	Discomfort with movement	Significant discomfort at rest	Emergency room visit or hospitalization
Erythema/Redness *	2.5 - 5 cm	5.1 – 10 cm	> 10 cm	Necrosis or exfoliative dermatitis
Induration/Swelling **	2.5 – 5 cm and does not interfere with activity	5.1 – 10 cm or interferes with activity	> 10 cm or prevents daily activity	Necrosis

^{*} In addition to grading the measured local reaction at the greatest single diameter, the measurement should be recorded as a continuous variable.

^{**} Induration/Swelling should be evaluated and graded using the functional scale as well as the actual measurement.

Version Number: 1.8 Date: July 26, 2019

Grade	Dose Modification	Management
Any Grade	For any grade: Per guidance below	 For any grade: Manage per institutional standard at the discretion of investigator. Monitor patients for signs and symptoms of administration site reactions. Educate patients on infection control.
Grade 1	For Grade 1: No changes in dose or schedule are recommended	 For Grade 1: Consider symptomatic treatment with over-the-counter analgesics and supportive care (i.e., cold compress)
Grade 2	For Grade 2: If persistent injection site reaction lasting more than 10 days despite optimal management, MEDI0457 next dose of vaccine should be omitted. Durvalumab to continue dependent on discussion of investigator with medial monitor. For second occurrence of Grade 2: In the setting of second occurrence of persistent ≥ Grade 2 injection site reaction for more than 7 days despite optimal medical management, permanently discontinue MEDI0457 and durvalumab.	 Symptomatic treatment with over-the-counter analgesics (opioids should be avoided unless necessary) and supportive care (i.e. cold compress) If pain persists for 3 days, contact investigator
Grade 3 or Grade 4	For Grade 3: Injection should be held until the toxicity resolves to Grade 1 or baseline. • If resolution occurs within 5 days, consider continued dosing of MEDI0457 and durvalumab at the current schedule as long as the adverse event of concern was not considered life threatening. • If the Grade 3 injection site toxicity only improves to Grade 2 within 5 days then omit next dose of MEDI0147 and continue durvalumab dependent on discussion of investigator with medical monitor. • If no change of Grade 3 reaction within 5 days, then permanently discontinue MEDI0457 and durvalumab. For Grade 4: Permanently discontinue MEDI0457 and durvalumab.	 For Grade 3 or Grade 4: Consult investigator for evaluation (rule out infection or other causes) and treatment (opioids may be considered) Obtain dermatology/surgical consult Consider hospitalization

Version Number: 1.8 Date: July 26, 2019

Proprietary of MD Anderson Cancer Center

APPENDIX F. DURVALUMAB WEIGHT-BASED DOSE CALCULATION

For durvalumab dosing done depending on subject weight. Weight-based dosing should be utilized for patients < 30 kg who would have otherwise received a 1500mg fixed dose.

- 1. Cohort dose: X mg/kg
- 2. Subject weight: Y kg
- 3. Dose for subject: XY mg = $X (mg/kg) \times Y (kg)$
- 4. Dose to be added into infusion bag:

Dose
$$(mL) = XY mg / 50 (mg/mL)$$

where 50 mg/mL is durvalumab nominal concentration.

The corresponding volume of durvalumab should be rounded to the nearest tenth mL (0.1 mL). Dose adjustments for each cycle are only needed for greater than 10% change in weight.

5. The number of vials required for dose preparation is the next greatest whole number of vials from the following formula:

Number of vials = Dose (mL) / 10.0 (mL/vial)

Example:

- 1. Cohort dose: 20 mg/kg
- 2. Subject weight: 30 kg
- 3. Dose for subject: $600 \text{ mg} = 20 \text{ (mg/kg)} \times 30 \text{ (kg)}$
- 4. Dose to be added into infusion bag:

Dose
$$(mL) = 600 \text{ mg} / 50 \text{ (mg/mL)} = 12.0 \text{ mL}$$

5. The number of vials required for dose preparation:

Number of vials = 12.0 (mL) / 10.0 (mL/vial) = 2 vials

Bagarazzi, M. L., Yan, J., Morrow, M. P., Shen, X., Parker, R. L., Lee, J. C., . . . Sardesai, N. Y. (2012). Immunotherapy against HPV16/18 generates potent TH1 and cytotoxic cellular immune responses. *Sci Transl Med*, 4(155), 155ra138. doi:10.1126/scitranslmed.3004414

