1.3.3.1. Rationale for fixed dosing

A population PK model was developed for durvalumab using monotherapy data from a Phase I study (Study 1108; N=292; doses=0.1 to 10 mg/kg Q2W or 15 mg/kg Q3W; solid tumors). Population PK analysis indicated only minor impact of body weight (WT) on the PK of durvalumab (coefficient of ≤ 0.5). The impact of body WT-based (10 mg/kg Q2W) and fixed dosing (750 mg Q2W) of durvalumab was evaluated by comparing predicted steady state PK concentrations (5th, median and 95th percentiles) using the population PK model. A fixed dose of 750 mg was selected to approximate 10 mg/kg (based on median body WT of ~75 kg). A total of 1000 subjects were simulated using body WT distribution of 40−120 kg. Simulation results demonstrate that body WT-based and fixed dosing regimens yield similar median steady state PK concentrations with slightly less overall between-subject variability with fixed dosing regimen.

Similar findings have been reported by others (Ng et al 2006, Wang et al 2009, Zhang et al 2012, Narwal et al 2013). Wang and colleagues investigated 12 monoclonal antibodies and found that fixed and body size-based dosing perform similarly, with fixed dosing being better for 7 of 12 antibodies (Wang et al 2009). In addition, they investigated 18 therapeutic proteins and peptides and showed that fixed dosing performed better for 12 of 18 in terms of reducing the between-subject variability in pharmacokinetic/pharmacodynamics parameters (Zhang et al 2012).

A fixed dosing approach is preferred by the prescribing community due to ease of use and reduced dosing errors. Given expectation of similar pharmacokinetic exposure and variability, we considered it feasible to switch to fixed dosing regimens. Based on average body WT of 75 kg, a fixed dose of 1500 mg Q4W durvalumab (equivalent to 20 mg/kg Q4W) is included in the current study.

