4.3.2. Durvalumab

All doses will be prepared in infusion bags under aseptic conditions by trained personnel; it should not be prepared on the ward. No incompatibilities between Durvalumab and polyvinylchloride or polyolefin IV bags have been observed.

Durvalumab will be administered using an IV bag containing 0.9% (w/v) saline, with a final Durvalumab concentration ranging from 1 to 20 mg/mL, and delivered through an IV administration set with a 0.2- or 0.22- μ m in-line filter.

For patients ≥30 kg, remove 30.0 mL of IV solution from the IV bag prior to addition of Durvalumab. Next, 30.0 mL of Durvalumab (i.e., 1500 mg of Durvalumab) is added to the IV bag such that final concentration is within 1 to 20 mg/mL (IV bag volumes 100 to 1000 mL). Mix the bag by gently inverting to ensure homogeneity of the dose in the bag.

For patients < 30 kg, calculate the dose volume of Durvalumab and number of vials needed for the subject to achieve the accurate dose according to **Appendix F**.

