4.4. Doses and Treatments

4.4.1. Planned Dosing Schedule

All patients will receive combination treatment with MEDI0457 and durvalumab as per the following **Planned Dosing Schedule** (treatment should be given at the beginning of the week, unless otherwise specified) as detailed in **Figure 1** and **Table 3**.

Durvalumab will be administered at a fixed dose of 1500 mg q4wk for patients that are \ge 30 kg. For patients who weigh <30 kg, weight-based dosing will be used at a dose of 20 mg/kg q 4 weeks, and if their weight increases to \ge 30 kg they can be switched to durvalumab at 1500 mg every 4 weeks.

Patients will receive 7 mg MEDI0457 delivered by IM followed by EP on Day 1 (Week 1), Week 3, Week 7, Week 12 and then every 8 weeks until disease progression or unacceptable toxicity. Durvalumab will be administered on Week 4, Week 8, Week 12 and then every 4 weeks until disease progression or unacceptable toxicity. On days when both MEDI0457 and durvalumab administrations will occur on the same day (Week 12 then every 8 weeks), MEDI0457 will be administered first, and durvalumab IV infusion will start approximately 1 hour after MEDI0457 is delivered intramuscularly followed by EP.

Minimum time between Week 3 MEDI0457 dose and the Week 4 first durvalumab dose, and the Week 7 MEDI0457 dose and the Week 8 durvalumab dose is 7 days.

Version Number: 1.8 Proprietary of MD Anderson Cancer Center Page 1019 26 2019

4.4.2. **Durvalumab**

Durvalumab will be administered at a fixed dose of 1500 mg q4w in the combination and monotherapy arms for patients weighing \geq 30 kg. For patients weighing \leq 30 kg, the dose will be 20 mg/kg. The maximum number of doses of checkpoint inhibitor therapy will equal 13.

The duration will be approximately 1 hour (± 5 minutes) for each durvalumab infusion. A 1- hour observation period is required after the first infusion of durvalumab is administered. If no clinically significant infusion reactions are observed during or after the first dose, subsequent infusion observation periods can be at the investigator's discretion (suggested 30 minutes after each durvalumab infusion).

Patients will be monitored during and after the infusion with assessment of vital signs at the times specified in the study protocol.

See Section 6.7.1 dose administration changes in the event of Grade 1 or 2 infusion-related reactions.

4.4.3. **MEDI0457**

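### The durvalumab weight rule is inconsistent at exactly 30 kg: the fixed-dose rule gives 1500 mg, while Section 4.4.2 as read and the Appendix F example also lead to 600 mg

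*Combined protocol and SAP*

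**What the plan says.** Four places in the protocol state or apply the weight rule for durvalumab.

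- **Section 4.4.1 (planned schedule).** The fixed 1500 mg dose every 4 weeks applies at 30 kg or more. For lighter patients: "For patients who weigh <30 kg, weight-based dosing will be used at a dose of 20 mg/kg q 4 weeks". A patient whose weight later reaches 30 kg may move to the fixed dose.
- **Section 4.3.2 (preparation).** The split is the same. At 30 kg or more, "30.0 mL of Durvalumab (i.e., 1500 mg of Durvalumab) is added to the IV bag". Only patients under 30 kg are sent to Appendix F.
- **Section 4.4.2 (durvalumab).** The fixed dose applies at 30 kg or more. The next sentence, as its sign reads in the available text, gives 20 mg/kg at 30 kg *or less*.
- **Appendix F (weight-based calculation).** It opens with its scope: "Weight-based dosing should be utilized for patients < 30 kg who would have otherwise received a 1500mg fixed dose". Its only worked example then sets "Subject weight: 30 kg" at 20 mg/kg.

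The rationale is in Section 1.3.3.1: "Based on average body WT of 75 kg, a fixed dose of 1500 mg Q4W durvalumab" is described as equivalent to 20 mg/kg every 4 weeks. On the supporting simulation, the section says: "A total of 1000 subjects were simulated using body WT distribution of" 40 to 120 kg.

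**The concern.** A weight cut-off has to put every weight in exactly one group. Here 30 kg appears on the fixed-dose side in some places and on the weight-based side in others, and the two sides lead to very different amounts of drug. The discrepancy sits in operative text: the schedule, the preparation instruction, and the worked calculation that someone preparing a dose may well follow. Sections 3.1 and 3.2 set no minimum weight, and Section 6.5.7 has weight measured at every visit, so the protocol provides for such a patient and would detect one. What is at stake is the dose of one product in an unusual patient. The trial's inference is not at stake.

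**Working it through.** **Inputs.** Dose rate 20 mg/kg (Sections 4.4.1 and 4.4.2, Appendix F). Fixed dose 1500 mg (Sections 4.3.2, 4.4.1 and 4.4.2). Concentration 50 mg/mL and vial volume 10.0 mL (Section 4.1.2, Appendix F).

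**Formulas (Appendix F).** Dose = mg/kg × kg. Volume = dose ÷ 50 mg/mL. Vials = volume ÷ 10.0 mL, rounded up.

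**1. The protocol's own figures.**
- Appendix F example: 20 × 30 = 600 mg; 600 ÷ 50 = 12.0 mL; 12.0 ÷ 10.0 = 1.2, rounded up to 2 vials. This matches.
- Section 4.3.2: 1500 ÷ 50 = 30.0 mL. This matches. The vial count is 30.0 ÷ 10.0 = 3.
- Section 1.3.3.1: 1500 ÷ 75 = 20 mg/kg. This matches.

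No calculation is wrong. The question is only which group 30 kg belongs to.

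**2. Where each place puts 30 kg.**

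| Place | Fixed 1500 mg | 20 mg/kg | Group for 30 kg |
|---|---|---|---|
| 4.3.2 | ≥ 30 kg | < 30 kg (via Appendix F) | Fixed |
| 4.4.1 | ≥ 30 kg | < 30 kg | Fixed |
| 4.4.2, as read | ≥ 30 kg | ≤ 30 kg | Both |
| Appendix F, opening line | – | < 30 kg | Not weight-based |
| Appendix F, example | – | applied at 30 kg | Weight-based |

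There are two separate conflicts: the overlap within Section 4.4.2, and the Appendix F example against that appendix's own scope and against Sections 4.3.2 and 4.4.1.

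**3. Size at 30 kg.** Fixed: 1500 mg, 30.0 mL, 3 vials. Weight-based: 600 mg, 12.0 mL, 2 vials. Ratio 1500 ÷ 600 = 2.5.

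**4. How far the conflict reaches.** At 29.9 kg every rule gives weight-based dosing (20 × 29.9 = 598 mg). At 30.1 kg every rule gives 1500 mg. The conflict is confined to 30 kg itself.

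**5. Side check on the rationale.** The simulated range starts at 40 kg and the fixed-dose rule starts at 30 kg. Weights from 30 to under 40 kg receive the fixed dose but lie outside the range that Section 1.3.3.1 describes.

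**The case against.** The strongest reply is that the working rule is clear. Sections 4.3.2 and 4.4.1 and the first line of Appendix F agree, and Section 4.4.1 also covers a patient who crosses the line. Someone who starts from Section 4.3.2 with a 30 kg patient is never sent to Appendix F. The example illustrates a formula with a round number and does not set a threshold. The overlap in Section 4.4.2 hangs on one sign in machine-read text, and that sign may have been misread.

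Much of this stands. The sign cannot be verified from the text available, and most of the passages do point the same way. But the example remains in conflict with its own appendix even if the sign is a reading error. A majority of passages is also no substitute for one consistent rule.

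Two stronger readings are tempting, and the documents do not support them.

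- *The fixed dose fails the protocol's own 20 mg/kg equivalence.* A reader might infer this from 1500 ÷ 30 = 50 mg/kg, or 1500 ÷ 40 = 37.5 mg/kg. But Section 1.3.3.1 ties the equivalence to an average of 75 kg, and any flat dose equals 20 mg/kg at one weight only. The section defends fixed dosing on predicted exposure (a weight coefficient of at most 0.5 and similar median steady-state concentrations), not on equal mg/kg at every weight. The 40 kg figure also lies at the edge of the simulated range and so is covered by it.
- *The jump from 598 mg at 29.9 kg to 1500 mg at 30.0 kg is an error.* It follows from the two-tier rule as written. Whether the cut-off is suitable is a clinical question, and its basis may lie in sources that are not available here.

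**Conclusion.** The inconsistency is real and minor. At exactly 30 kg the protocol supports both 1500 mg and 600 mg, which differ 2.5-fold; at every other weight its passages agree on the group. The finding does not depend on how the sign in Section 4.4.2 is read, because the Appendix F example conflicts with the stated scope by itself. That the case will seldom arise is an assumption: the trial enrols adults, and the documents give no weight distribution for the patients expected. Sample size, error rates and the primary analysis are unaffected.

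The gap between the simulated range (from 40 kg) and the fixed-dose rule (from 30 kg) is a side note. It shows that the simulation described in Section 1.3.3.1 does not reach weights from 30 to under 40 kg. It does not show that the dose there is wrong.

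**What to change.** Reconcile Sections 4.3.2, 4.4.1 and 4.4.2 and Appendix F so that 30 kg falls in one group only, with the same inequality sign used throughout. Check the sign in Section 4.4.2 against the source file. Make the worked example in Appendix F use a weight inside the range it illustrates, and recompute its dose, volume and vial lines if the weight changes.

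Separately, reconcile Section 1.3.3.1 with the fixed-dose rule, or state what supports the fixed dose from 30 to under 40 kg.

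The choice of group, dose and cut-off is the sponsor's, and none is proposed here. The cost is a few words, possibly one replaced example, and a sentence in the rationale. No design or analysis change follows.
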